## **Adverse Events**

No severe adverse events have been reported of previously used versions of ESTAIR with people with complex trauma, including in randomised controlled trials (Cloitre et al, 2010). However, we wish to improve the recording and reporting of adverse effects of psychological interventions and have therefore developed a robust protocol for assessing and managing any such risk, which will be completed at end of treatment and at follow-up. The Adverse Events Questionnaire (AEQ; Hutton et al., 2015) was initially developed to investigate adverse effects of a psychosis-specific intervention and was adapted for the present study by removing any psychosis-specific items.

The AEQ used in the present study consists of 25 items (e.g., worsening of mental state, heightened stigma, increased medication use), which are responded to on a 5-point scale ranging from “Not at all” to “Very much”. All participants completing the ESTAIR intervention will complete the trial-completer, patient-rated version of the AEQ. To improve on the reporting of adverse events, participants who withdraw from the study will be asked to complete the early-withdrawal version of the AEQ together with the therapist.

Using an approach applied previously (adapted from Klingberg et al., 2012), we will define serious adverse events as (i) death by suicide; (ii) suicide attempt; (iii) suicidal crisis without attempt; (iv) severe symptom exacerbation (increase of 2 standard deviations or more on the patient or researcher-rated ITQ. Non-severe adverse events will be defined as a score of  $\geq 3$  (agree ‘quite a lot’ or ‘a lot’) on any item on the AEQ (Hutton et al., 2015).

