### **Study Suspension or Discontinuation**

The research project would be stopped in the event of several therapy-attributable adverse events. Any serious adverse events will be passed on to trial management group for review, who would have responsibility for assessing whether they are attributable to study participation, setting the threshold for discontinuation and issuing advice to suspend or discontinue. This advice would be acted upon by the researchers, in consultation with the Sponsor.

ESTAIR participants will continue treatment until (1) the clinical aims have been met, where the clinician deems 'reliable recovery' has occurred, or (2) the criteria for withdrawal have been met (4 or more missed sessions).

**Update note:** The criteria for withdrawal has been extended to include if participants do not attend 4 or more sessions in total or two continuous sessions, in the absence of any exceptional circumstances.

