#### ***Management of disclosures (harm to self or others)***

The study involves questions about traumatic stress, which is associated with self-harm. As people will have regular contact with a clinician for their treatment, an imminent risk of harm to self or others will already be known and managed appropriately. However, in some cases the clinical team may not be aware of this risk. In all cases, participants will be informed that their data will be held confidentially but if they disclose information which suggests an imminent risk of harm to them or someone else, then the research team are obliged take steps to reduce this risk, which in most cases will involve them sharing their concerns immediately with their GP who will then take over the clinical management. The research assistant will act at all times under supervision of an experienced clinical psychologist in assessing and managing this process, ensuring both they and the participant are fully supported and safe.

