## **Ethical considerations and good clinical practice**

### ***Ethical Conduct***

This study will be conducted in accordance with the principles of the International Conference on Harmonisation Tripartite Guideline for Good Clinical Practice (ICH GCP). Before the study commences, all required approvals will be obtained and any conditions of approvals will be met.

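### The serious adverse event list is closed and non-severe events exist only as AEQ scores, so a death not ruled suicide is in neither class and other major harms may go uncounted, especially in TAU

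*Combined protocol and SAP*

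**What the plan says.** The Adverse Events section sets up two classes of event.

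- Serious: "we will define serious adverse events as (i) death by suicide; (ii) suicide attempt; (iii) suicidal crisis without attempt; (iv) severe symptom exacerbation". Item (iv) is then specified as an "increase of 2 standard deviations or more on the patient or researcher-rated ITQ". Nothing in the sentence marks the four items as examples, and no catch-all follows.
- Non-severe: "Non-severe adverse events will be defined as a score of" 3 or more on any AEQ item. No other way of becoming a non-severe event is given.

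On the form itself: "The AEQ used in the present study consists of 25 items (e.g., worsening of mental state, heightened stigma, increased medication use". The other 22 items are not shown. On who fills it in: "All participants completing the ESTAIR intervention will complete the trial-completer, patient-rated version of the AEQ". Participants who withdraw are asked to complete an early-withdrawal version with the therapist. TAU participants who remain in the study are not mentioned.

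Other sections deal with what happens to events:

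- Participant Withdrawal or Discontinuation has the clinician report adverse events to the trial management group. The group reviews all of them, attributable or not, and may withdraw the participant or suspend or stop the trial. An update note adds escalation of risk concerns to senior staff, safeguarding leads and the MDT.
- Study Suspension or Discontinuation says that "Any serious adverse events will be passed on to trial management group for review". Its stopping sentence refers to several therapy-attributable adverse events, without the word serious.
- Management of disclosures (harm to self or others) notes that "The study involves questions about traumatic stress, which is associated with self-harm" and sends disclosed imminent risk to the GP.

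The Data analysis section contains no tabulation or analysis of adverse events.

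**The concern.** A safety definition has to be able to place the events that the population may plausibly have. Here the only two classes are a closed list centred on suicide and symptom worsening, and a score on a questionnaire. A death by accident, from alcohol or from an overdose of undetermined intent fits neither. Self-harm without suicidal intent, admission to hospital and violence to others are not named at all, although the protocol has a section on disclosure of harm to self or others.

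Two things are at stake. First, the pilot could report that there were no serious adverse events when a participant had died. The Progression Criteria for a Full Trial contain no safety element, so nothing downstream would test that statement before it was carried into the full trial. Second, non-severe events cannot be compared between arms if only one arm's completers are given the instrument that defines them.

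**Working it through.** The documents state no event rate, expected count or safety precision, so there is no figure of the plan's own to reproduce. The main check is to apply the definitions in the Adverse Events section to each kind of event.

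| Event | Serious, items (i) to (iv)? | Non-severe: ESTAIR completer or any participant who withdraws | Non-severe: TAU participant who stays in |
|---|---|---|---|
| Death not ruled suicide | The death itself: no | No: the participant cannot rate the form | No |
| Non-suicidal self-harm | Not named; only if (ii) to (iv) is also met | Only if one of the 22 unseen items covers it | No AEQ assigned |
| Hospital admission | Not named; only if (ii) to (iv) is also met | Only if one of the 22 unseen items covers it | No AEQ assigned |
| Serious harm to others | Not named; only if (ii) to (iv) is also met | Only if one of the 22 unseen items covers it | No AEQ assigned |

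The first row follows from the text alone. The other rows depend on AEQ content that cannot be seen (25 items, 3 shown, 25 − 3 = 22 not shown). Even where an unseen item fits, the rule would label an admission or an assault non-severe.

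Next, does any other section supply the missing rule? The sections on withdrawal, suspension and disclosures say who is told and who decides. None redefines an adverse event, says how an event outside the two classes is recorded, or says that it is reported.

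For scale only, take n = 30 per arm from the Sample size section and assume counts of 0 and 1. Exact (Clopper-Pearson) 95% limits:

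- 0/30: lower limit 0; upper limit 1 − 0.025^(1/30) = 0.1157, so 0% (0 to 11.6%).
- 1/30: lower limit 1 − 0.975^(1/30) = 0.0008; upper limit is the p that solves (1 − p)^30 + 30p(1 − p)^29 = 0.025, giving p = 0.1722. So 3.3% (0.1 to 17.2%).

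The chance that at least one unclassified event occurs among all 60 participants is 1 − (1 − p)^60, where p is an assumed per-participant probability:

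| Assumed p | Chance of at least one in 60 |
|---|---|
| 1% | 45% |
| 2% | 70% |
| 5% | 95% |
| 10% | 99.8% |

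**The case against.** The strongest reply is the clinician-report route under Participant Withdrawal or Discontinuation. It starts from a clinician noticing an event, not from an end-of-treatment score. It is not confined to serious events, and it gives the trial management group power to suspend or stop. A clinician reporting in real time cannot be waiting for an AEQ. This stands. A reader might infer from the closed list that events outside it need not be passed on and cannot count towards stopping. The documents do not support that: review covers all adverse events, and the stopping sentence speaks of therapy-attributable adverse events rather than serious ones. What the reply does not supply is a classification, a count or a reporting rule.

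A reader might also infer that every admission or act of self-harm counts as zero serious events. That is too strong. One that accompanies a suicide attempt, a suicidal crisis or a 2 SD rise on the ITQ falls under items (ii) to (iv), and an unseen AEQ item may pick up others in ESTAIR as non-severe.

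It is tempting to add a conflict with the commitment that the study be "conducted in accordance with the principles of the International Conference on Harmonisation Tripartite Guideline for Good Clinical Practice (ICH GCP". The documents do not reproduce that guideline's definition of a serious event, so they cannot show a conflict, and the point does not need one.

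The section opens by giving end of treatment and follow-up as the time points for its safety protocol, without naming an arm. It could be said that TAU is implied. The sentence that assigns the AEQ, however, names ESTAIR completers only. Finally, the serious event list is declared as adapted from an approach applied before. That explains where it came from but does not close the gap.

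**Conclusion.** The point holds in a limited form and should be acted on. It is certain from the text that a death not ruled suicide is in neither class, so the written rule gives a wrong safety count if followed. Non-suicidal self-harm, hospital admission and serious harm to others are not named as serious and may be uncounted. How often depends on overlap with items (ii) to (iv) and on AEQ items that are not shown. The gap is widest for TAU participants who stay in, who have no AEQ and so no written route to a non-severe event. Such events may well be seen and handled clinically; the defect lies in classification, counting and reporting.

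The size cannot be estimated from the documents. The intervals and probabilities above rest on assumed counts and rates, and show only that in arms of 30 a single misplaced event visibly changes the safety statement.

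**What to change.** In the Adverse Events section, keep items (i) to (iv) and add recording lines for:

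- death from any cause;
- unplanned hospital admission, including psychiatric admission;
- self-harm regardless of intent;
- serious harm to others.

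Apply them to both arms, from randomisation to the 12-week follow-up, whether or not an AEQ is returned. Take the information from clinician reports, from any service records that are available, and from the research assistant's existing contacts with participants at 25 weeks and at follow-up. Report the added lines by arm and separately from (i) to (iv), so that comparison with the earlier approach is kept. Reconcile the definitions with the reviews described under Participant Withdrawal or Discontinuation and Study Suspension or Discontinuation, so that one meaning of adverse event runs through all three sections. This is a recording and reporting rule; withdrawal and stopping decisions stay with the trial management group.

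The cost is a short protocol amendment, extra lines on the event form and a few questions at contacts already planned. The documents do not say whether Combat Stress records hold admissions or harm to others, so those records should not be the only source. The downside is a few more events to log and review, and a count that looks less favourable.

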## **Qualitative outcomes**

Qualitative data will be collected to explore the acceptability of the ESTAIR intervention. It was initially intended to invite a total of 4 completers and 4 non-completers from the ESTAIR arm to participate in a one-off qualitative interview. In order to enhance understanding of the acceptability of ESTAIR and to manage feasibility concerns, it was decided that all participants in the ESTAIR arm would be asked to answer specific, brief questions assessing their experience of the protocol, their perception of treatment in general, and suggestions for improvement.

**Update Note:** Given concerns that the specific questions administered to all participants completing the ESTAIR intervention would not provide rich enough data to infer the acceptability of the ESTAIR protocol, two safeguards are put in place for collecting qualitative data. Prior to completing the self-report qualitative questions, the research assistant will call participants to explain purpose of the qualitative items and will explain that responses will be anonymised by participant number and that they will not be shared with the therapist. If at the end of collection of qualitative data, responses do not appear rich enough to answer research questions 3 and 4, efforts will be made to recruit an independent research assistant/assistant psychologist to administer the one-off interviews to 4 completers and 4 non-completers from the ESTAIR arm. This will be done by an independent research assistant/assistant psychologist to reduce biases in interview responses, should they be required.

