## **AIMS**

ICD-11 CPTSD is a new condition and there are currently no identified effective treatments to enable recovery from this debilitating condition. Identifying effective interventions to treat veterans with CPTSD is therefore of paramount importance. We have recently proposed in the research literature a new innovative person-centred treatment approach for CPTSD (i.e. modular therapy; Karatzias and Cloitre, 2020). Enhanced Skills Training in Affective and Interpersonal Regulation (ESTAIR) involves targeting the symptoms of CPTSD clusters sequentially using concrete modules (i.e. specific number of sessions targeting specific clusters of symptoms). This intervention has never been tested in a military population before.

The project will provide information on recruitment and acceptability of a new treatment for CPTSD. The following main research questions will be addressed as part of this pilot project:

- I. Is it feasible to recruit for a study on ESTAIR vs. TAU in military personnel during the study recruitment period?
- II. What is the retention rate in the study at the end of treatment and at 3-month follow-up?
- III. Are primary and secondary outcomes acceptable from participants?
- IV. Is the new ESTAIR protocol acceptable by people with CPTSD?

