### **Treatment as Usual (TAU)**

At present there are no recommended treatments for CPTSD. TAU will normally consist of receiving a mental health assessment by either a psychiatrist or psychologist. Following this, a treatment package will be developed that could include elements of psychoeducation, symptom-management, and trauma-focused cognitive behaviour therapy. Details of TAU interventions delivered for all participants in the TAU will be recorded.

**Update Note:** TAU will consist of receiving a mental health assessment by a mental health professional.

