## OUTCOME MEASURES

Outcomes are as follows: **(i)** Retention & data completion rates at weeks 25 weeks post-treatment and 12-week follow-up, on the primary outcome; International Trauma Questionnaire (Cloitre et al., 2018) and secondary outcomes: PHQ Depression (Kroenke et al., 2001), GAD Generalised Anxiety (Spitzer et al., 2006), AUDIT Substance Misuse (Saunders et al., 1993), and PHQ-15 Medically Unexplained Symptoms (Kroenke et al., 2002) **(ii)** 12-month recruitment rate; **(iii)** participant & clinical staff views on trial & intervention acceptability and suggested changes. Baseline information on demographics including age, gender, marital status etc., will be gathered to characterise the sample.

A range of assessments will be administered by the research assistant to test the acceptability of primary (PTSD and CPTSD) (i.e. ITQ) and secondary outcomes (depression, anxiety, alcohol use, and somatisation) (e.g. GHQ-12, AUDIT). Participants in both groups will be asked to complete these outcome measures at baseline, after 25-weeks post-treatment and then again after at a 12-week follow-up. The ITQ will be also completed by the ESTAIR group at the end of every module. In addition, data will be recorded on retention and DNA rate. The research assistant will be masked to group allocation to demonstrate to future funders this is achievable in a future trial.

**Note:** The ITQ will be completed by the therapist and participant at the end of every model. Due to feasibility concerns, the research assistant will not be masked to group allocation when collected measures at baseline, post-treatment, and follow-up. This is not expected to have any impact on outcomes as all primary and secondary outcome measures are self-report.

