### **Somatic Symptoms**

Medically unexplained symptoms will be assessed using the *Patient health Questionnaire-15* (PHQ-15; Kroenke et al., 2002). The scale includes the most prevalent DSM-IV somatization disorder somatic symptoms. Participants are required to rate the severity of 13 symptoms as 0 (“not bothered at all”), 1 (“bothered a little”), or 2 (“bothered a lot”). Responses are coded as 0 (“not at all”), 1 (“several days”), or 2 (“more than half the days” or “nearly every day”) to produce total scores ranging from 0 to 30 and scores of  $\geq 5$ ,  $\geq 10$ ,  $\geq 15$  represent mild, moderate and severe levels of somatization. The reliability and validity of the PHQ-15 are acceptable.

**Update Note: Friends and Family Test (FFT).** The FFT was added as an additional secondary measure to help infer the acceptability of the ESTAIR intervention in comparison to TAU. The FFT is a single item asking participants to indicate ‘how likely is it that you would recommend our service to your GP, family and friends if they needed similar care?’. Responses are indicated on a 5 point-Likert scale ranging from 1 (‘Extremely unlikely’) to 5 (‘Extremely likely’). The FFT is standardly administered as an end-of-treatment measure at Combat Stress.

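### Participants' views on the measures and the trial are sought only from the ESTAIR arm, so in TAU research question III rests on retention and completion data alone; the FFT comparison with TAU has no stated trial time point and no analysis

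*Combined protocol and SAP*

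**What the plan says.** All references are to the combined protocol and SAP.

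- **AIMS.** Question III is "Are primary and secondary outcomes acceptable from participants". Question IV is separate: "Is the new ESTAIR protocol acceptable by people with CPTSD".
- **OUTCOME MEASURES.** Outcome (iii) is "participant & clinical staff views on trial & intervention acceptability and suggested changes", with no restriction by arm. Outcome (i) is retention and data completion on the ITQ and the secondary measures. The section also says "A range of assessments will be administered by the research assistant to test the acceptability of primary" and secondary outcomes, and that "Participants in both groups will be asked to complete these outcome measures at baseline, after 25-weeks post-treatment" and again at the 12-week follow-up.
- **Qualitative outcomes.** Here "all participants in the ESTAIR arm would be asked to answer specific, brief questions assessing their experience of the protocol". The Update Note treats these responses as the material for questions 3 and 4. If they prove too thin, the fallback is interviews with 4 completers and 4 non-completers, all from ESTAIR.
- **PROCEDURE.** The research assistant contacts participants at 25 weeks for post-intervention measures, without limit by arm. The request for qualitative data at that point goes to ESTAIR only.
- **Qualitative analyses.** The data to be summarised concern acceptability of both the intervention and the outcomes.
- **Somatic Symptoms, Update Note on the FFT.** The FFT was added to help judge ESTAIR's acceptability against TAU. On timing, the note says only: "The FFT is standardly administered as an end-of-treatment measure at Combat Stress".
- **Treatment as Usual (TAU), Update Note.** "TAU will consist of receiving a mental health assessment by a mental health professional".
- **Quantitative analyses, Phase 2.** The between-arm regression lists the ITQ, PHQ-9, GAD-7, PHQ-15 and AUDIT. The FFT is not among them.

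**The concern.** Question III is about the measures, not the therapy, and TAU participants complete those measures on the same schedule. Outcome (iii) also promises views on the trial and suggestions for change. Every described way of obtaining participants' views nevertheless stops at the ESTAIR arm, while the protocol counts on the resulting data for question III.

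The pilot is meant to show whether a larger trial with the same kind of control can recruit and retain. How people respond to being randomised to that control, and then being asked for repeated trauma questionnaires, is something only TAU participants can report. If nobody asks them, the full trial would be designed without that information.

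The FFT raises a smaller, related problem. It is the one measure added expressly to compare acceptability between the arms, but the only timing described for it belongs to the service's end-of-treatment routine, and no end of treatment is defined for TAU.

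**Working it through.** The plan states no acceptability figure, margin or power, so there is nothing of that kind to reproduce. The check is mainly a comparison of sections, followed by simple counts.

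**1. Scope of the question against scope of collection**

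| Item | Arms covered |
|---|---|
| Question III (AIMS) | not restricted |
| Outcome (iii), views on trial and intervention (OUTCOME MEASURES) | not restricted |
| Outcome measures completed (OUTCOME MEASURES) | both |
| Retention and completion, outcome (i) | both |
| Brief questions (Qualitative outcomes) | ESTAIR |
| Fallback interviews (Qualitative outcomes) | ESTAIR |
| Qualitative request at 25 weeks (PROCEDURE) | ESTAIR |
| FFT (Update Note) | both implied, TAU time point not stated |

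Because question IV already deals with ESTAIR, question III cannot sensibly be read as a question about ESTAIR alone. The mismatch therefore lies within the plan.

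**2. Coverage**

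Sample size gives 30 per arm, and 30 + 30 = 60 agrees with the stated total.

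- Asked for views, ESTAIR: at most 30 of 30. This is an upper limit, because the Update Note under Qualitative outcomes speaks of those completing ESTAIR rather than of all in the arm.
- Asked for views, TAU: 0 of 30.
- Overall: at most 30/60 = 50% of those randomised.
- Retention and completion data: planned for 60 of 60.

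**3. What each source can show**

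Completion data show whether forms came back. They do not show why forms were missed, whether those that were returned felt burdensome, or what participants would change. The FFT asks whether the person would recommend the service, so it does not address the measures or the trial procedures either.

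**4. Precision, for scale only**

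Assume an acceptability answer is coded yes or no, with the least favourable proportion, p = 0.5. The 95% half-width for one proportion is 1.96 × √(0.25/n), and for a difference between two arms of n each it is 1.96 × √(2 × 0.25/n).

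- One arm, n = 30: ±17.9 points. Both arms pooled, n = 60: ±12.7 points.
- With 75% responding (the level in the progression criterion, 0.75 × 60 = 45): ±14.6 points pooled. With about 22 in a single arm: ±20.9 points.
- Difference between arms: ±25.3 points at 30 per arm, ±29.5 points at 22 per arm.

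An FFT contrast at this size can only be descriptive. The gain from asking TAU is mainly that the arm is heard at all, and only secondarily that the pooled estimate is tighter.

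**The case against.** The strongest reply is that question III already has a planned route in both arms. OUTCOME MEASURES says the assessments are given to test the acceptability of the outcomes, both groups complete them, and data completion is a named outcome. Recruitment and Retention summarises these rates, and the progression criterion uses 25-week ITQ data from everyone randomised. Qualitative outcomes opens by tying the qualitative work to acceptability of ESTAIR, and the protocol aims to keep assessment burden low. In a pilot of 60, confining qualitative work to the new treatment is a defensible choice.

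Much of this stands, and it rules out three stronger conclusions that a reader might draw.

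- *That no TAU feedback is planned at all.* The documents do not support this. Completion data cover both arms, and an FFT added for comparison with TAU is implicitly to be collected there, most naturally at the 25-week contact.
- *That the FFT would be missing for every TAU participant.* This requires both that the FFT be given only when a therapy course ends and that TAU have no such end. The sentence on timing describes service routine and does not restrict use in the trial. The documents also do not speak with one voice on TAU content: the Update Note describes an assessment, while the main TAU text and step 4 of Recruitment refer to a treatment package or standard treatment. Those passages need reconciling, and neither reading can be taken as settled.
- *That question III would be answered by the half of the sample more favourable to the measures.* Nothing in the documents shows that therapy recipients judge questionnaire burden more kindly, and the completion data come from all 60.

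What the reply does not remove is the protocol's own reliance on ESTAIR-only responses for question III, and an outcome (iii) that promises views on the trial and suggested changes without limiting them to one arm.

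**Conclusion.** The point holds as a gap in coverage that is cheap to close. It does not threaten the validity of the trial. Following the plan as written, no TAU participant is asked directly about the measures, randomisation or trial procedures, so question III is answered in that arm by retention and completion data only and outcome (iii) is met for one arm at best.

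The FFT part is a matter of missing detail: TAU collection is implied, but the trial time point and the analysis are not stated.

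The conclusion assumes the planned 30 per arm is recruited and that no route for TAU views exists beyond those described. It does not depend on any assumption about how TAU participants would answer.

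**What to change.** 1. At the existing 25-week contact, ask every randomised participant in both arms the same few written questions on acceptability of the outcome measures, of randomisation and of the trial procedures, including suggested changes. Keep the questions about the therapy for ESTAIR.
2. Give the FFT to both arms at that same contact, whether or not treatment was received or finished, and state this in the Update Note and under PROCEDURE.
3. Add both items to the analysis section. Report responses by arm, with numbers asked and numbers answering. Summarise the FFT descriptively with confidence intervals and without a hypothesis test.
4. State under Qualitative outcomes which data answer question III and which answer question IV.

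The cost is a few minutes' extra burden for TAU participants and slightly more free text to code. No visit is added and no treatment changes.
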